4.4.2.4.3 Duration

Duration will be computed using the same methodology as for unsolicited non-serious AEs described in Section [4.4.2.2.5](#).

4.4.2.5 Other Safety Endpoints

4.4.2.5.1 Pregnancy

This information will be listed as collected. No derivation or imputation will be done.

4.4.2.5.2 Action Taken

This information will be summarized as collected, including missing observations. No derivation or imputation will be done.

4.4.2.5.3 Seriousness

This information will be summarized as collected. No derivation or imputation will be done.

4.4.2.5.4 Outcome

This information will be summarized as collected. No derivation or imputation will be done.

4.4.2.5.5 Causality

There are 3 terms in our study indicating if there is a causal relationship between an AE and study vaccine (MenACYW conjugate vaccine, Trumenba vaccine, and Bexsero vaccine). It includes

“Relationship to Investigational Medicinal Product (IMP)” which refers to the relationship with MenACYW conjugate vaccine, “Relationship to Non-Investigational Medicinal Product (non-IMP)” which refers to the relationship with Trumenba vaccine or Bexsero vaccine, and “Relationship to Study Procedures” which is applicable for SAEs only. This information will be summarized as collected.

Variable “Relationship” which stands for the overall relationship and encompasses the “Relationship to IMP” and “Relationship to Study Procedures” will be derived in the tables and listings according to the following rules in this study:

- For all solicited reactions, the overall relationship will be derived as “Related”
- For all unsolicited injection site reactions, the overall relationship will be derived as “Related”
- For unsolicited non-serious systemic AEs,
If “Relationship to IMP” is ticked as “Related” or missing, the overall relationship should be derived as “Related”; otherwise the overall relationship should be derived as “Not Related”.
- For unsolicited serious systemic AEs,
If any of “Relationship to IMP” and “Relationship to Study Procedures” is ticked as “Related” or missing, the overall relationship should be derived as “Related”; otherwise the overall relationship should be derived as “Not Related”.

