3. Percentage of subjects with titer $\geq 1:8$ and $\geq 1:128$ and 95% CI
4. Percentage of subjects with titer ≥ 4 -fold rise from pre-vaccination to post-vaccination, and 95% CI
5. Percentage of subjects with rSBA vaccine seroresponse*

*rSBA vaccine seroresponse is defined as a post-vaccination titer $\geq 1:32$ for subjects with pre-vaccination rSBA titer $< 1:8$, or a post-vaccination titer ≥ 4 times the pre-vaccination titer for subjects with pre-vaccination rSBA titer $\geq 1:8$.

Data from subjects from MET50 (or MET43, if applicable) and MET59 will be combined and paired to evaluate antibody persistence and overall trends over 3-6 years post-priming with an MCV4 (ie, MenACYW conjugate vaccine-primed subjects or Menveo vaccine-primed subjects). If Menveo vaccine primed subjects that were not part of MET50 are recruited, those will not contribute to the assessment of antibody persistence.

Additional subgroup analyses of the hSBA vaccine seroresponse rates, hSBA titer $\geq 1:4$ and $\geq 1:8$, hSBA GMTs, rSBA vaccine seroresponse rates, rSBA titer $\geq 1:8$ and $\geq 1:128$, and rSBA GMTs will also be provided by number of years (3 years, 4 years, 5 years, and 6 years) elapsed since

priming vaccination received in either clinical studies MET50, MET43, or outside of Sanofi Pasteur trials, age group (13 to 17 years and 18 to 26 years), gender (Female and Male), and race (White, Asian, Black or African American, and Other).

Safety

Safety analysis will include but is not limited to the following:

1. The number and percentage of subjects reporting any solicited injection site reactions and solicited systemic reactions occurring from D0 to D07 after each vaccination will be summarized by study group for intensity, time of onset period, days of occurrence, and action taken. Since MenACYW conjugate vaccine and the concomitant MenB vaccines will be administered in different limbs, solicited injection site reactions can be distinguished between the two products, and will be analyzed and presented separately.
2. Immediate unsolicited systemic AEs and unsolicited AEs occurring up to D30 after each vaccination will be summarized.
3. The number and percentage of subjects reporting any unsolicited non-serious AEs will be summarized by study group, intensity, time of onset period, duration, and by MedDRA preferred term and system organ class (SOC), as well as by relationship to the study vaccine.

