4.3.2.2 Safety Endpoints

The observational endpoints for the evaluation of safety are:

- 1) Occurrence, nature (Medical Dictionary for Regulatory Activities [MedDRA] preferred term), duration, intensity, and relationship to vaccination, and whether the event led to early termination from the study, of any unsolicited systemic AEs reported in the 30 minutes after vaccination(s)

- 2) Occurrence, time of onset, number of days of occurrence, intensity, action taken, and whether the reaction led to early termination from the study, of solicited (prelisted in the subject's diary card and CRB) injection site reactions occurring up to D07 after vaccination(s)
- 3) Occurrence, time of onset, number of days of occurrence, intensity, action taken, and whether the reaction led to early termination from the study, of solicited (prelisted in the subject's diary card and CRB) systemic reactions occurring up to D07 after vaccination(s)
- 4) Occurrence, nature (MedDRA preferred term), time of onset, duration, intensity, action taken, relationship to vaccination (for systemic AEs only), and whether the event led to early termination from the study, of unsolicited AEs up to D30 after vaccination(s)
- 5) Occurrence, nature (MedDRA preferred term), time of onset, duration, seriousness criteria, relationship to vaccination, outcome, and whether the event led to early termination from the study, of SAEs (including AESIs) after vaccination(s) from D0 through the end of the trial
- 6) Occurrence, nature (MedDRA preferred term), time of onset, duration, seriousness criteria, relationship to vaccination, outcome for MAAEs from D30 visit to the 6-month follow-up contact. MAAEs will be collected as unsolicited AEs up to the D30 (+ 14 days) visit

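### The SAP's derived overall relationship omits the MenB vaccine, so an unsolicited systemic AE in Groups 3 and 4 attributed only to the D0 MenB dose is reported as Not Related

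*SAP*

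**What the plan says.** SAP 4.4.2.5.5 treats MenACYW, Trumenba and Bexsero all as study vaccine and names three collected causality items:

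- relationship to the IMP, meaning MenACYW;
- relationship to the non-IMP, "which refers to the relationship with Trumenba vaccine or Bexsero vaccine";
- relationship to study procedures, for SAEs only.

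Of these it says "This information will be summarized as collected".

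It then introduces an additional variable, Relationship, "which stands for the overall relationship and encompasses the “Relationship to IMP” and “Relationship to Study Procedures” will be derived". This variable "will be derived in the tables and listings according to the following rules in this study". The rules are:

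- Solicited reactions and unsolicited injection site reactions are always *Related*.
- For unsolicited non-serious systemic AEs: "If “Relationship to IMP” is ticked as “Related” or missing, the overall relationship should be derived as “Related"; otherwise *Not Related*.
- For unsolicited serious systemic AEs, the same test is applied to the IMP and study procedures items together.

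The non-IMP item appears in neither systemic rule. SAP 5.3.1.2, on missing causality, only points back to this section.

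Protocol 12.1.3 plans summaries of unsolicited non-serious AEs and of SAEs "as well as by relationship to the study vaccine".

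**The concern.** Groups 3 and 4 exist to describe MenACYW given together with a MenB vaccine. Under these rules, a systemic event that the investigator attributes to the MenB injection given at D0, and not to MenACYW, appears as unrelated in any output that uses the overall variable. Groups 1 and 2 receive no MenB vaccine, so only the co-administration groups are affected.

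For events starting before any further MenB dose, the error has one direction: it can only lower the related percentage with MenB, and so make co-administration look closer to MenACYW alone than the investigators judged it to be.

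Missing answers are also handled unevenly. A blank IMP answer counts as *Related*, a blank MenB answer is ignored, and so is a positive MenB attribution.

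The SAP also does not say which MenB dose the non-IMP answer refers to. Later MenB doses, from D30 and at D180, are outside the study's scope (Protocol 1.4 and 5.1.3; SAP 1 and 3.2), yet SAEs and MAAEs are analysed to D180 (+14 days).

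**Working it through.** The plan states no figure to reproduce here. The check is to apply the SAP 4.4.2.5.5 rules to every answer pattern, then repeat with the MenB item added under the same related-or-missing test.

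**Non-serious systemic AEs: IMP × non-IMP, 3 × 3 = 9 patterns**

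| IMP | non-IMP | SAP rule | With non-IMP added |
|---|---|---|---|
| Related or missing | any (6 patterns) | Related | Related |
| Not related | Related | **Not Related** | **Related** |
| Not related | missing | **Not Related** | **Related** |
| Not related | Not related | Not Related | Not Related |

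One pattern gives the wrong answer (IMP not related, non-IMP related). One more shows the uneven handling of missing answers. In all, 2 of 9 patterns change.

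**Serious systemic AEs: IMP × non-IMP × study procedures, 3 × 3 × 3 = 27 patterns**

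The same two cases change, both with IMP and study procedures not related: 2 of 27. The other 25 are identical. These are counts of patterns, not event frequencies.

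**Size in subjects**

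- Exposed groups: (100 + 100) / 600 = 33.3% of planned subjects.
- One affected subject with no other related AE: 1/100 = 1 percentage point within Group 3 or Group 4; 1/200 = 0.5 point in the two groups pooled.
- The documents give no rate of MenB-only attribution. As an assumed range, 1 to 10 such subjects among 200 would understate the pooled related percentage by 1/200 = 0.5 to 10/200 = 5.0 points.

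**Where the identity of the MenB dose matters** (calendar days, not shares of events)

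- Non-serious AEs are analysed for onset D0 to D30, which is 31 days. The earliest planned later MenB dose is D30, and exclusion criterion 3 bars planned receipt of other vaccines before then, influenza vaccine excepted. D0 to D29 is 30 days: 30/31 = 97%. The dose question hardly arises here.
- SAEs run from D0 to D180, which is 181 days. D30 onward is 151/181 = 83%, or 165/195 = 85% with the +14-day window. This is an upper bound, because the D30 dose is optional and the visit may fall up to 14 days later.

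**Which outputs are reached.** The rules cover the event types in three rows of SAP Table 5.2: immediate AEs, unsolicited non-serious AEs and SAEs. The discontinuation row overlaps these. The MAAE row is an inference, because SAP 4.4.2.4 gives no separate causality derivation. Table 5.2 does not say which relationship variable each row uses.

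**The case against.** The strongest defence is that the variable was meant to concern MenACYW. Protocol 9.3.2.3.3 and 9.3.2.4, and SAP 4.3.2.3.3 and 4.3.2.4, speak of causality with respect to the investigational product. The protocol lists the MenB vaccines under other products (6.2). The safety objective is framed around the MenACYW booster. The SAP says which items the variable contains, and its rules follow that statement, so the exclusion may be deliberate.

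That defence does not fit the variable as written. It takes in study procedures, so a procedure-related SAE is *Related* while one attributed to the MenB vaccine is not. It makes every injection site reaction *Related*, including those at the MenB site, although Protocol 12.1.3 notes that "solicited injection site reactions can be distinguished between the two products". Injection site reactions are related by convention, so that second point is the weaker of the two. The label *overall* and the inclusion of procedures carry more weight. The definition of *Related* in Protocol 9.3.2.7 and SAP 4.3.2.7 refers to the product administered, and the MAAE sections (Protocol 9.3.2.5, SAP 4.3.2.5) are wider than the IMP.

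Several points for the other side do stand. The MenB item is still summarised as collected, so the attribution is not lost. No particular table can be shown to be wrong. With both vaccines given at one visit, investigators may often tick both, so the MenB-only cell could be small. Adding the item also requires knowing which MenB dose was meant for later events. These points limit the consequence, but they do not correct the derived variable.

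**Conclusion.** Wrong as written, and worth fixing. The overall relationship misses MenB-only attributions of unsolicited systemic AEs, serious and non-serious, in Groups 3 and 4. For events before D30 this can only understate relatedness. From D30 onward the direction is uncertain, because some MenB attributions may concern out-of-scope doses.

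The number of affected events is unknown; the percentage-point figures assume that affected subjects have no other related AE. Overall AE and SAE incidence is untouched, solicited and injection site reactions are unaffected, and no hypothesis test depends on the variable.

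**What to change.** **Preferred change.** In both unsolicited systemic AE rules of SAP 4.4.2.5.5, add a condition: in Groups 3 and 4, the event is also *Related* if the non-IMP answer is related or missing with respect to the MenB dose given at D0. Restrict it to those groups, so that a field left blank by design in Groups 1 and 2 does not count as missing. Tying it to D0 agrees with SAP 4.4.2.2.3 and 4.4.2.3.1, which already fix D0 as the last vaccination. List separately any event attributed only to a later MenB dose.

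**If a variable restricted to MenACYW is intended.** Rename it as relationship to MenACYW (and, for SAEs, study procedures). State how MenB-site reactions are classified, and show relatedness to the D0 MenB dose beside it in every Group 3 and 4 output that reports relationship.

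In either case, Table 5.2 should name the relationship variable used in each row.

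**Cost.** One extra condition in each of two rules, using an item already collected. Events starting on or after D30 in Groups 3 and 4 need a check of which MenB dose the answer refers to. Related percentages in those groups may rise slightly.

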4.4.2.5.6 Adverse Events Leading to Study Discontinuation

A flag is available in the clinical database for all AEs in order to identify AEs leading to study discontinuation.

In general, the items that are counted are:

- Disposition table: A subject who has, on the termination form, the reason for early termination “Serious Adverse Event” or “Other Adverse Event” is checked
- Safety overview table: A subject who has either the reason for early termination “Serious Adverse Event” or “Other Adverse Event” checked or lists an AE on an AE page (solicited, unsolicited, or SAE) that has “Reaction Leading to Termination” or “Event Leading to Termination” or “Serious Adverse Event Leading to Termination” checked on the termination form, that is at least Grade 1 and is within the time period indicated
- System Organ Class/Preferred Term (SOC/PT) table: An event (solicited, unsolicited, or SAE) that has “Reaction Leading to Termination” or “Event Leading to Termination” or “Serious Adverse Event Leading to Termination” checked that is at least Grade 1 and is within the time period indicated

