4.4.2.2 Unsolicited Non-serious Adverse Events

4.4.2.2.1 Presence

An observation will be considered an event if it has at least a verbatim term and is not Grade 0 (None) intensity event.

Grade 0 events will not be included in the analysis of the endpoint and should be included in the listing “Unsolicited non-serious adverse events not included in the safety analysis.”

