4.4.2.2.2 Intensity

Intensity for unsolicited non-serious AE will be derived according to the following classification:

Grade 0 (None), Grade 1, Grade 2, Grade 3, or Missing (Unknown).

If the unsolicited non-serious AE is measurable and its preferred term is part of the list of solicited reactions, then the measurement is derived based upon and following the same rule as the intensity scales defined in the Section [4.4.2.1.1](#) for that measurable injection site or systemic reaction.

Intensity for the other unsolicited non-serious AEs will correspond to the value reported in the CRF.

The maximum intensity corresponds to the highest intensity for a unique term.

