4.4.2.3.2 Time of Onset

Time of onset will be computed using the same methodology than for unsolicited non-serious AEs described in Section 4.4.2.2.4.

SAEs (including AESIs) will be analyzed throughout the study using the following periods:

- Within 7 days after vaccination(s)
- Within 30 days after vaccination(s)
- During 6-month follow-up period: from D31 to the last telephone call on D180 (+ 14 days)
- During the entire study period: from D0 to the last telephone call on D180 (+ 14 days) (ie, all SAEs [including AESIs] occurred during the study)

An SAE (including AESI) with missing time of onset will be considered to have occurred just after the vaccination indicated by the visit number, so will be included in these tables.

Note: SAEs (including AESIs) that occurred before vaccination (negative time of onset) will not be included in analysis, but will be listed separately.

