5.3.1.4 Intensity

For solicited reactions, missing intensities will be handled as described in Section 4.4.2.1.1. For unsolicited non-serious AEs, missing intensities will remain missing and will not be imputed.

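### The SOC/PT table of AEs leading to study discontinuation leaves out unsolicited AEs and SAEs with a missing grade, although the SAP counts them as events elsewhere

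*SAP*

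**What the plan says.** SAP 4.4.2.5.6 gives three counting rules for discontinuation due to AEs.

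- **Disposition.** The rule is "Disposition table: A subject who has, on the termination form, the reason for early termination" marked as a serious or other adverse event. Grade plays no part.
- **Safety overview.** A subject counts by either of two routes: that same termination reason, or an AE-page entry (solicited, unsolicited or SAE) with the leading-to-termination item "checked on the termination form, that is at least Grade 1 and is within the time period indicated".
- **SOC/PT table.** An event counts if its leading-to-termination item is "checked that is at least Grade 1 and is within the time period indicated". There is no alternative route.

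For unsolicited non-serious AEs in general, SAP 4.4.2.2.1 says: "An observation will be considered an event if it has at least a verbatim term and is not Grade 0 (None) intensity event". The only exclusion by grade there is that "Grade 0 events will not be included in the analysis of the endpoint". SAP 4.4.2.2.2 makes missing (unknown) an intensity category of its own, and SAP 5.3.1.4 adds: "For unsolicited non-serious AEs, missing intensities will remain missing and will not be imputed".

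For SAEs, SAP 4.4.2.3.2 sets no grade condition; its whole-study period covers "all SAEs [including AESIs] occurred during the study". For solicited reactions, SAP 4.4.2.1.3 takes Grade 1 to 3 as presence and a missing intensity as missing presence.

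**The concern.** Requiring at least Grade 1 and excluding Grade 0 sound like the same rule, but they differ when the grade is blank. SAP 4.4.2.5.6 uses the first and SAP 4.4.2.2.1 the second. An event that ended a subject's participation can thus be in the unsolicited AE or SAE tables and missing from the table whose purpose is to say which events led to discontinuation. A reader of the study report could see a subject counted as discontinued for an AE in the disposition and overview tables and find no matching term in the SOC/PT table.

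Discontinuations for AEs after a single vaccination visit are likely to be few, so one omitted event would be visible. What is at stake is the completeness of a descriptive safety table, not any inference.

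**Working it through.** The plan gives no figure to reproduce. The check applies each counting rule to each intensity category, for an event flagged as leading to termination and inside the time window.

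| Event type | Grade | Counted as an event in its own section? | In the SOC/PT discontinuation table (4.4.2.5.6)? |
|---|---|---|---|
| Unsolicited non-serious AE (4.4.2.2.1) | 0 | No | No |
| | 1, 2 or 3 | Yes | Yes |
| | Missing | **Yes** | **No** |
| SAE (4.4.2.3.2) | 1, 2 or 3 | Yes | Yes |
| | Missing | **Yes** | **No** |
| Solicited reaction (4.4.2.1.3) | None | No | No |
| | 1, 2 or 3 | Yes | Yes |
| | Missing | No (missing presence) | No |

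For unsolicited non-serious AEs the rules part only in the missing category, and no imputation rule moves such an event into Grade 1 or higher. A missing grade on an SAE has the same consequence. Solicited reactions show no conflict.

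Next, take a subject whose only flagged event is an unsolicited AE or SAE with a missing grade.

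| Termination reason | Disposition | Overview | SOC/PT table |
|---|---|---|---|
| AE or SAE | Counted | Counted, through the reason | **Event absent** |
| Other | Not counted (reason only) | **Not counted** | **Event absent** |

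The filter therefore binds always in the SOC/PT table, in the overview only when the recorded reason is not an AE, and never in disposition.

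**Size of one omission.** This takes the planned n = 100 of Group 3 or Group 4 as the denominator and uses exact (Clopper-Pearson) 95% limits.

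- As shown, 0/100: the upper limit is 1 − 0.025^(1/100) = 3.62%, so 0% (0 to 3.6).
- With the event kept, 1/100: the lower limit is 1 − 0.975^(1/100) = 0.025%. The upper limit solves (1 − p)^100 + 100p(1 − p)^99 = 0.025, giving 5.45%. So 1% (0.03 to 5.5).

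This is the effect of one event if it occurs. The documents give no rate of missing grades, so no expected number can be computed.

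**The case against.** The strongest reply is that the situation should hardly arise and that the event would still be visible.

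- SAP 4.3.2.3.3 requires intensity for every unsolicited AE, serious or not, and the row of SAP Table 5.2 for AEs leading to discontinuation lists intensity.
- An AE that causes discontinuation must be followed until it resolves, stabilises or becomes chronic (Protocol 5.1.4). Missing information must be explained (11.1), checks look for omissions (11.2), and queries must be completed before lock (13.4.1).
- Protocol 5.2.10 ranks Adverse Event first among termination reasons, so the subject would normally remain in the disposition and overview tables.
- SAP Table 5.2 also reports study discontinuation in the unsolicited AE and SAE rows, with no grade screen stated there.
- SAP 4.4.2.5.6 introduces its rules as general ones, and its grade condition was plausibly meant only to remove Grade 0.

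All of this stands as an argument that the effect is small. None of it supplies a rule that a missing grade counts as Grade 1 or higher, and a programmer who follows the text will drop the event.

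Four stronger readings are tempting, and the documents do not support them.

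- **SAEs as a class fall out because they carry no grade.** The derivation in SAP 4.4.2.2.2 is for non-serious AEs and the SAE row of Table 5.2 omits intensity, but SAP 4.3.2.3.3 has intensity recorded for SAEs too. Only an SAE with a blank grade is affected.
- **Missing grades are never imputed.** SAP 5.3.1.4 says so for unsolicited non-serious AEs only. SAP 4.4.2.1.1 does derive some solicited intensities, such as Grade 3 for a reaction too large to measure.
- **The event vanishes from the safety report.** It remains in the AE or SAE tables and, with an AE termination reason, in disposition and overview.
- **Aligning the grade rule would make overview and SOC/PT tables agree.** The overview can count a subject from the termination form alone, so the two can differ for other reasons.

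**Conclusion.** The inconsistency is real and narrow. As written, SAP 4.4.2.5.6 excludes an unsolicited AE or SAE with a missing grade from the SOC/PT table of AEs leading to discontinuation. It also excludes it from the AE-page route of the safety overview, which matters when the termination reason is not an AE. SAP 4.4.2.2.1 and 4.4.2.3.2 would count the same event.

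The consequence is limited to descriptive safety tables and is probably rare. One omission would change a displayed 1% to 0% in Group 3 or 4, in the SOC/PT table. That figure assumes the planned group size and that such an event occurs at all. Disposition, the primary analysis and power are unaffected. This is a worthwhile clarification, not a threat to the trial's conclusions.

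**What to change.** In the overview and SOC/PT bullets of SAP 4.4.2.5.6, replace the single grade condition by one for each event type:

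- unsolicited non-serious AEs: not Grade 0, with a missing grade kept and shown as missing, in line with 4.4.2.2.1;
- SAEs, including AESIs: counted whatever their recorded grade, in line with 4.4.2.3.2;
- solicited reactions: Grade 1 to 3 as now, in line with 4.4.2.1.3.

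A blanket change to *not Grade 0* should be avoided. Both bullets also cover solicited reactions, so it would admit those with missing intensity, which 4.4.2.1.3 treats as missing presence.

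The cost is a short wording change and one condition in the table program. No new data, no added subjects and no change to any hypothesis are needed.
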